4.2 Initial Registration

Eligible patients will be registered on study centrally at UT Southwestern Medical by the Lead Site Study Coordinator.

To register a patient, the following documents must be completed and emailed at [contact] M—F 8am to 5pm CST.

- Signed/dated patient consent form
- Eligibility checklist
- Copies of pre hormone therapy/chemotherapy or radiation therapy
- Screening labs(including pregnancy test)/vital signs and EKG
- CT reports
- Other materials may also be sent if considered pertinent for confirming patient eligibility, e.g. CT/MRI of C/A/P

The Lead Center will review the documents to confirm eligibility. To complete the registration process the Lead Center will:

- Assign a patient study number
- Patients found to be ineligible for participation after being consented will be considered screen failures, and documented as such in the Screening and Enrollment Log
- New subjects will receive a number beginning with 001 upon study consent such that the first subject consented is numbered 001, the second subject consented receives the number 002, etc.
- Upon confirmation of eligibility and enrollment as per the afore-mentioned instructions, the subject will be assigned a secondary number in the order of enrollment. For example, subject 001 will become 001-01 upon enrollment. If subject 002 screen fails, and subject 003 is the next subject enrolled, subject 003 will become 003-02 and so-on.
- For UTSW, each newly consented subject should be numbered using the schema provided above. Upon registration, the registrar will assign the additional registration/randomization code according to the numbering schema outlined above, which should then be entered as the patient study id in Velos upon updating the status to enrolled.

- The numbering schema should clearly identify the site number; the sequential number of the subject enrolled as well as the status of the subjects enrolled so that the number of subjects consented versus the number of subjects actually enrolled may be easily identified.

4.3 Study Calendar

The Investigator may perform more frequent examinations than shown in Table below if clinically indicated. Data from such additional examinations are also to be reported in the eCRF.

* baseline visit and W1D1 can be combined	Screening	Baseline Visit*	Induction Phase Cycle ^a 1 and 2				Maintenance Phase Cycle ^a 3 and every subsequent cycle (8 weeks) (up to 2 years)		30 day Follow-up ^r (X1)	Follow-up Visits ^s (X2 and X3)	Survival Follow-Up ^t
	D -28 to 0	D-3 to D 1	W1D1* (C1W1)	W4D1 (C1W4)	W7D1 (C2W1)	W10D1 (C2W4)	W1D1	W5D1			
Informed consent	X										
Inclusion/Exclusion Criteria	X ^p										
Archival Tumor Tissue ^b	X										
Nivolumab ^c			X	X	X	X	X	X			
Ipilimumab ^d			X	X	X	X					
SBRT ^e			X ^e								
Medical history	X	X									
Physical assessment	X	X	X	X	X	X	X	X	X	X	
Vital signs ^f	X	X	X	X	X	X	X	X	X	X	
Height	X										
Performance status ^g	X	X	X	X	X	X	X	X	X	X	
Pulse Oximetry ^h			X	X	X	X	X	X			
EKG	X										
Adverse Events Assessment			X	X	X	X	X	X	X	X	
Concomitant Medications	X	X	X	X	X	X	X	X	X	X	
Disease Assessment ⁱ	X	every 6 weeks (\pm 1 wk) for the first 13 months from treatment and every 12 weeks (\pm 1 wk) thereafter, until disease progression is documented or treatment is discontinued (whichever occurs later)									
CBC with diff ^j	X	X ^q	X	X	X	X	X	X	X	X	
Comp Panel ^k	X	X ^q	X	X	X	X	X	X	X	X	

TSH, free T4, free T3 ^u	X	X ^q	X	X	X	X	X	X		X		
Pregnancy test ^l	X	X	X	X	X	X	X	X		X	X	
	Screening	Baseline Visit	Induction Phase Cycle ^a1 and 2				Maintenance Phase Cycle^a 3 and every subsequent cycle (8 weeks) (up to 2 years)			30 day Follow-up ^r (X1)	Follow-up Visits^s (X2 and X3)	Survival Follow-Up ^t
	D-28 to 0	D-3 to D1	W1D1 (C1W1)	W4D1 (C1W4)	W7D1 (C2W1)	W10D1 (C2W4)	W1D1	W5D1				
Hep B or Hep C ^m	X											
Research biopsy ⁿ	X				X					X		
Blood sample ^o	X				X					X		
Survival Follow-Up ^t												X

a. 1 cycle = 6 weeks
 b. Archival Formalin-fixed paraffin-embedded (FFPE) tumor tissue must be available for correlative studies (Note: Fine Needle Aspiration [FNA] and bone metastases samples are not acceptable for submission)
 c. Nivolumab is to be administered as an approximately 60-minute IV infusion. Cycle 1 of maintenance will begin 3 weeks after the 4th dose of induction therapy or after Day 113 if the 4th dose of induction therapy has not been administered due to treatment delays or the discontinuation of combination therapy because of primarily ipilimumab related side effects
 d. Ipilimumab is to be administered as an approximately 30-minute IV infusion. When both study drugs are to be administered on the same day, separate infusion bags and filters must be used for each infusion. Nivolumab is to be administered first.
 e. SBRT (5 fractions of 10 Gy) is to be delivered anytime between Day 1 of Week 1 (Cycle 1) and Day 1 of Week 4 (Cycle 1) of the nivolumab and ipilimumab combination dosing (within the first 3 weeks after the initiation of nivolumab and ipilimumab). SBRT is preferred to be delivered in the first 2 weeks.
 f. Temp, Pulse, B.P., Weight
 g. Karnofsky Performance Status
 h. Oxygen saturation by pulse oximetry should be obtained prior to dosing (at rest and with exertion) Also perform if any new or worsening pulmonary symptoms present
 i. CT with contrast of the chest, abdomen, pelvis and all known sites of disease (or CT Chest w/o contrast and MRI of abdomen with or without contrast if reduced GFR or allergy). MRI (preferred) or CT scan of the Brain if known history of brain involvement (all known sites of disease should be assessed at baseline)
 j. CBC w/differential and platelets
 k. Full Chemistry Panel including: LDH, AST, ALT, ALP, T.Bili, BUN, creatinine, Ca+, Mg+, Na-, K+, HCO3-, Cl-, glucose, albumin, T.Protein, amylase, lipase
 l. WOCBP only (serum or urine) at screening and within 24 hours of dosing
 m. HepB sAg & HCV Ab or HCV RNA
 n. Multiple tumor biopsies – pre-treatment (optional), at week 7 of treatment (optional) and at the time of progression (optional)
 o. Blood samples will be collected for research at pre-treatment, at week 7 of treatment and at the time of progression
 p. Prior to entry into the protocol, all patients need to be discussed with [name] (JHU), [name] (UTSW) or co-investigator Radiation Oncologist from the Radiation Therapy Department to determine eligibility/feasibility for SBRT. The cancer lesion(s) to be radiated should be determined by the Radiation Oncologist in collaboration with the Principal Investigator/Medical Oncologist
 q. Cycle 1 Day 1 labs do not need to be performed if done \leq 72 hours of dosing as part of the Day -3 to +1 labs
 r. Perform 30 days \pm 1 week from last dose of study drug

- s. X2 will take place 8 weeks (+/- 1 week) after last dose of nivolumab was administered and visit X3 will take place 15 weeks (+/- 1 week) after last dose of nivolumab was administered. If additional X follow-up visits are required due to ongoing study drug-related toxicity, they should take place every 8 weeks (+/- 1 week) until study drug-related toxicity has resolved, stabilized or been deemed irreversible.
- t. Study subjects will be contacted every 3 months for survival data. Other potential data such as the subjects' follow-up treatment or care may be requested during these contacts. The contacts can be via telephone or correspond with disease assessment visits or other scheduled visits
- u. Free T3 & Free T4 if TSH not within normal limits

4.4 Safety Assessments / Considerations

At baseline, a medical history will be obtained to capture relevant underlying conditions. The baseline examinations should include weight, height, Karnofsky Performance Status, BP, HR, and temperature. Baseline signs and symptoms are those that are assessed within 28 days prior to treatment. Concomitant medications will be collected from within 28 days prior to treatment.

Baseline local laboratory assessments should be done within 28 days prior to treatment to include: CBC w/differential, LFTs (ALT, AST, total bilirubin, alkaline phosphatase), BUN or serum urea level, creatinine, Ca, albumin, Mg, Na, K, Cl, LDH, glucose, amylase, lipase, TSH, Free T4, Free T3, and Hep B and C testing (HBV sAg, HCV Ab or HCV RNA).

Pregnancy testing for WOCBP must be performed within 24 hours prior to the initial administration of study drug at baseline and then every 4 weeks during the treatment period and at the safety follow-up visits. After discontinuation from nivolumab these should be repeated at approximately 30 days and approximately 70 days [or more frequently if required by local standard]. If, following initiation of the investigational product, it is subsequently discovered that a study **subject is pregnant or may have been pregnant** at the time of investigational product exposure, including during at least 6 half lives after product administration, the investigational product will be permanently discontinued in an appropriate manner (eg, dose tapering if necessary for subject safety). The investigator must immediately notify Worldwide Safety @BMS of this event via the Pregnancy Surveillance Form in accordance with SAE reporting procedures. Follow-up information regarding the course of the pregnancy, including perinatal and neonatal outcome and, where applicable, offspring information must be reported on the Pregnancy Surveillance Form [provided upon request from BMS]. Any pregnancy that occurs in a female partner of a male study participant should be reported to BMS. Information on this pregnancy will be collected on the Pregnancy Surveillance Form.

On study local laboratory assessments should be done within 72 hours of dosing to include; CBC w/differential, LFTs (ALT, AST, total bilirubin, alkaline phosphatase), BUN or serum urea level, creatinine, Ca, Mg, Na, K, Cl, LDH, glucose, amylase, lipase, TSH with reflexive Free T4, Free T3 on Day 1 of Weeks 1 and 4 for Cycles 1 and 2 and on Day 1 of Weeks 1 and 5 starting from Cycle 3. Additional measures including non-study required laboratory tests should be performed as clinically indicated or to comply with local regulations. Laboratory toxicities (eg, suspected drug induced liver enzyme elevations) will be monitored during the follow-up phase via on site/local labs until all study drug related toxicities resolve, return to baseline or are deemed irreversible. In addition, LFTs should also be assessed prior to the second dose of each cycle. The results of these labs should be reviewed prior to dosing. Amylase, Lipase and thyroid tests must be drawn, but do not need to be resulted prior to infusion unless patient is symptomatic. The following laboratory abnormalities should be documented and reported appropriately:

- any laboratory test result that is clinically significant or meets the definition of an SAE
- any laboratory abnormality that required the subject to have study drug discontinued or interrupted
- any laboratory abnormality that required the subject to receive specific corrective therapy.

Oxygen saturation by pulse oximetry should be obtained prior to each dosing and at any time a subject has any new or worsening respiratory symptoms. A reading at rest

and on exertion should be obtained at each time point. The extent of the exertion should be based on the judgment of the investigator, but should remain consistent for each individual subject throughout the study. If the patient's status changes, the investigator can alter the extent of exertion based on their medical judgment. If a subject shows changes on pulse oximetry or other pulmonary related signs (hypoxia, fever) or symptoms (eg, dyspnea, cough, fever) consistent with possible pulmonary adverse events, the patient subject should be immediately evaluated to rule out **pulmonary toxicity**. An algorithm for the management of suspected pulmonary toxicity can be found in the appendix of the nivolumab Investigator's Brochure.

Some of the previously referred to assessments may not be captured as data in the CRF. They are intended to be used as safety monitoring by the treating physician. Additional testing or assessments may be performed as clinically necessary or where required by institutional or local regulations.

Overdose: An overdose is defined as the accidental or intentional administration of any dose of a product that is considered both excessive and medically important. All occurrences of overdose must be reported as an SAE.

Other Safety Considerations: Any significant worsening noted during interim or final physical examinations, electrocardiograms, x rays, and any other potential safety assessments, whether or not these procedures are required by the protocol, should also be recorded as a nonserious or serious AE, as appropriate, and reported accordingly.

4.5 Imaging Assessment for the Study

Any incidental findings of potential clinical relevance that are not directly associated with the objectives of the protocol should be evaluated and handled by the Study Investigator as per standard medical/clinical judgment.

4.5.1 CT/MRI

Both, contrast-enhanced Computed Tomography (CT) and Magnetic Resonance Imaging (MRI) scans acquired on dedicated CT/MRI equipment are adequate imaging modalities for this study.

CT scans should be acquired with 5 mm slices with no intervening gap (contiguous). Subjects who cannot receive IV contrast at the start of study should be imaged by MRI

of abdomen/pelvis with IV contrast and CT of chest without contrast. MRIs should be acquired with 5 mm slices with no intervening gap (contiguous). Subsequent assessments should include chest, abdomen, and pelvis, and all known sites of disease and should use the same imaging method as was used at baseline. Patients initially imaged with CT of chest, abdomen, and pelvis with IV contrast who can no longer receive contrast can be monitored by CT of chest, abdomen, and pelvis without IV contrast. Every attempt should be made to image each subject using an identical acquisition protocol on the same scanner for all imaging time.

4.5.2 MRI/CT Brain

MRI (preferred) or CT of brain (with contrast) is required at screening only when metastatic disease to the brain is suspected or known. MRI or CT brain scans during on-study treatment and follow up periods are required only if clinically indicated for new signs and symptoms that suggest CNS involvement or progression.

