2.3 Study Population

For entry into the study, the following criteria MUST be met.

2.3...1 Inclusion Criteria

Eligibility waivers are not permitted. Subjects must meet all of the inclusion and exclusion criteria to be registered to the study. Study treatment may not begin until a subject is registered

1) *Signed Written Informed Consent*

- Willing and able to provide informed consent

2) *Target Population*

- Histological confirmation of RCC with a clear-cell component
- Metastatic (AJCC Stage IV) RCC
- Prior adjuvant or neoadjuvant therapy for localized or locally advanced RCC is allowed provided recurrence occurred = or > 6 months after the last dose of the adjuvant or neoadjuvant therapy
- Any number of prior systemic treatment regimen in the advanced/metastatic setting is allowed (cytokine, anti-angiogenic, mTOR inhibitor or clinical trial) including previously untreated patients
- Karnofsky Performance Status (KPS) of at least 70%
- Life expectancy of at least 3 months
- At least 2 metastatic sites of which at least 1 must be measurable as per RECIST 1.1

- Archival Formalin-fixed paraffin-embedded (FFPE) tumor tissue must be available for correlative studies (Note: Fine Needle Aspiration [FNA] and bone metastases samples are not acceptable for submission)
- Patients with favorable, intermediate and poor risk categories will be eligible for the study. *Patients must be categorized according to favorable versus intermediate/poor risk status at registration. International Metastatic RCC Database Consortium (IMDC) must be used to determine prognostic factors (Appendix 1)*

2.3.2 Exclusion Criteria:

1) Target Disease Exceptions

- Subjects with previously treated brain or CNS metastases are eligible provided that the subject has recovered from any acute effects of radiotherapy and is not requiring steroids, and any whole brain radiation therapy was completed at least 4 weeks prior to study drug administration, or any stereotactic radiosurgery was completed at least 2 weeks prior to study drug administration. Liver metastases will not be included as part of the radiated lesions to be treated.

2) Medical History and Concurrent Diseases

- Prior treatment with an anti-PD-1, anti-PD-L1, anti-PD-L2, anti-CD137, or anti-CTLA-4 antibody, or any other antibody or drug specifically targeting T-cell co-stimulation or checkpoint pathways. Prior treatment with HD IL-2 is allowed.

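### Section 4.5.2 makes on-study brain imaging symptom-driven even for patients with known brain metastases, while 4.5.1 calls for all known sites at every assessment, so a PR can be recorded with a known site not re-imaged

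*Combined protocol and SAP*

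**What the plan says.** - **Eligibility (2.3.2, Target Disease Exceptions).** "Subjects with previously treated brain or CNS metastases are eligible provided that the subject has recovered" and meets the further conditions listed there.
- **General imaging rule (4.5.1).** "Subsequent assessments should include chest, abdomen, and pelvis, and all known sites of disease", using the baseline imaging method. No exception is made for the brain.
- **Brain imaging rule (4.5.2).** At screening, a brain MRI or CT "is required at screening only when metastatic disease to the brain is suspected or known". After that, "MRI or CT brain scans during on-study treatment and follow up periods are required only if clinically indicated for new signs and symptoms"; the sentence goes on to specify symptoms that point to CNS involvement or to its progression.
- **Study calendar (4.3), footnote i.** The footnote belongs to the Disease Assessment row, which covers screening, then every 6 weeks for 13 months, then every 12 weeks. It lists "CT with contrast of the chest, abdomen, pelvis and all known sites of disease" and adds "MRI (preferred) or CT scan of the Brain if known history of brain involvement (all known sites of disease should be assessed at baseline".
- **Response scoring (4.6.3 to 4.6.9).** Lesions in a previously irradiated area are non-measurable unless documented as new since the radiation. Table 8 requires every non-target lesion to have disappeared for CR. Table 9 asks only for a non-target status of Non-PD for PR and has no row for a site that was not evaluated. Any new lesion is PD (4.6.8 and Table 9).

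**The concern.** For an asymptomatic patient with known brain metastases, one section calls for a brain scan at each scheduled assessment and the next does not require one. ORR is a primary endpoint and is judged by response counts. Best overall response is the investigator's determination, the trial runs at two sites, and the documents describe no central review that would bring the two readings together. Identical patients could be imaged and scored differently, and the gap works one way only: progression that is not looked for leaves an extracranial PR standing and delays the progression date.

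**Working it through.** No sample-size or power figure is involved. The check sets the sections side by side, with one line of arithmetic for scale.

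1. **Same patient, two sections.** Take a patient with treated brain metastases at baseline, no new CNS signs or symptoms, at any scheduled assessment.

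| Section | Brain imaged at this assessment? |
|---|---|
| 4.5.1 | Yes: a known site, by the baseline method |
| 4.5.2 | Not required |
| 4.3, footnote i | Leans to yes, but not conclusive (step 3) |

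2. **Does 4.5.2 reach this patient?** Yes. Its screening sentence deals with disease that is suspected or already known, and its on-study sentence mentions progression, which presupposes existing CNS disease. It cannot be read as covering only patients with a clear brain at entry.

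3. **What footnote i adds.** It sits on a row that spans all assessments and names brain imaging where there is a history of brain involvement. Its closing parenthesis, however, speaks of baseline, and nearly the same wording appears in the 4.1 flow chart on the screening/baseline row. It supports 4.5.1 but could not carry the point alone. The clear follow-up requirement is in 4.5.1.

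4. **Does scoring catch the gap?** Irradiated brain metastases are non-measurable under 4.6.3, so they are followed as non-target disease. For PR, Table 9 needs Non-PD there, and nothing says how to enter a site that was not imaged. The missing-assessment rule in 4.6.9 covers patients with no response assessment because of rapid progression or toxicity, not one unassessed site. The confirmation scan at 6 weeks or later (4.6.10) has the same gap. For CR, Table 8 read strictly is a barrier, because an un-imaged lesion has not been shown to disappear.

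5. **Direction.** If intracranial progression is present but unseen, a PR is kept that PD would have prevented, and DOR, TTP and PFS run on until symptoms prompt a scan. This includes new brain lesions. The opposite error does not arise from this gap.

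6. **Scale of one patient.** Section 9.3 stops after stage 1 at 6 or fewer responses of 15 and declares success at 17 or more of 25.
   - Stage 1: 1/15 = 6.7 points.
   - End of study: 1/25 = 4.0 points, if all 25 are in the denominator.
   - One patient can separate 6 from 7 of 15, or 16 from 17 of 25.

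**The case against.** The strongest reply is that 4.5.2 is the dedicated brain section and states what is required, while 4.5.1 is general and says what assessments should include. On that reading symptom-triggered imaging was a deliberate choice, and scheduled scans are a design preference. This is plausible, but 4.5.1 makes no exception for the brain and neither section refers to the other. Even if 4.5.2 was meant to prevail, the scoring rules still need to say what an un-imaged known site counts as.

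Second, 4.6.7 says that PD declared only on non-target change, with SD or PR in target lesions, will be extremely rare. That stands for growth of the treated lesions and makes the effect smaller. It does not cover new brain lesions, which are PD under 4.6.8 whatever the target lesions do.

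Third, the time-to-event endpoints are only described by Kaplan-Meier (9.5), so no decision rests on them. That is correct. Decisions rest on the ORR counts.

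Fourth, a rule that withholds PR whenever any known site was not imaged could remove genuine responses. That also stands, and the fix is drawn more narrowly for that reason.

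**Conclusion.** The contradiction between 4.5.1 and 4.5.2 is in current text and affects patients whom the protocol admits. It matters where a site follows 4.5.2 and the patient has no new CNS symptoms. The direction then favours the regimen, firmly for PR and for the dating of progression. The size cannot be estimated from the documents and may be nil if few or no such patients enrol.

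Three stronger readings are tempting and are not supported:

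- **That CR is equally exposed.** Table 8 requires disappearance of all non-target lesions, so a strict reader would not assign CR without a brain scan.
- **That the plan scores a missing brain scan as Non-PD.** No section says so, and Table 9 is offered only as an aid. The documents leave the case open.
- **That a number of false responders can be given.** Suppose 5 to 15% of 25 patients have brain metastases (1.25 to 3.75, roughly 1 to 4), 40 to 70% respond outside the brain, and 20 to 40% progress silently before confirmation. The product runs from 1 × 0.4 × 0.2 = 0.08 to 4 × 0.7 × 0.4 = 1.12 patients, or 0.3 to 4.5 points of ORR. All three inputs are assumptions with no source in the documents, so this range is not evidence of bias.

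**What to change.** 1. **Reconcile 4.5.1, 4.5.2 and footnote i.** Limit the symptom-driven sentence in 4.5.2 to subjects without known brain disease at baseline, so that known brain sites follow the 4.5.1 assessment schedule. Reword the closing parenthesis of footnote i so that it does not suggest baseline only.
2. **Add a scoring rule to 4.6.9.** A known brain site that was not imaged at an assessment is recorded as not evaluated, not as Non-PD, and CR is not assigned at that assessment.
3. **Add a sensitivity report.** Report ORR also with any PR that rests on such an assessment counted as a non-response. The main analysis then keeps genuine PRs, and the reader can see how much depends on the gap.

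**Cost.** This is a wording amendment that adds no scan beyond those 4.5.1 already calls for. At a site that had been following 4.5.2 it does mean extra brain scans for the affected subjects: 13 months is about 56 weeks, and 56/6 is about nine scheduled assessments per subject in that period. A few assessments will carry a not-evaluated entry.
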